4.2.1. Main Analytical Approach

The main estimand to answer the clinical question of the study is described in Section 1.1.

The frequency of moderate to severe HF and the change from baseline as well as the relative change (%) from baseline will be summarized using descriptive statistics (see Section 4.1) by treatment group and by week. Descriptive table will include participants on study treatment (a participant needs to have taken at least one dose of study drug during the week to be shown in the table). Post-treatment data will be used in the model-based analysis and shown in the listing only. The change from baseline over time in the frequency of HFs will be shown using line plots for means together with 95% CIs by treatment group.

Inference about the primary endpoints will be done based on a mixed model for repeated measures (MMRM). Prior to performing modeling with the MMRM, missing data will be handled in alignment with the estimand strategies for ICEs (described in Section 1.1).

Table 4–3 provides a detailed overview of the MMRM model for the change from baseline in frequency of HF. One of the stratification factors used at randomization, population type, will not be included in the analysis model because almost all participants are in the same category.

version 3.0 Page: 30 of 87

Table 4-3: Model description

Dependent variable:	Change from baseline in frequency of moderate to severe HF at Week 1, Week 4, Week 8 and Week 12
Covariates (continuous variables):	Baseline mean daily frequency of HF
Factors (class variables):	Treatment, Week
Stratification factor (class variables):	Type of treatment of pre-existing condition at baseline (tamoxifen or aromatase inhibitor)
Interaction terms:	Baseline*Week, Treatment*Week
Covariance structure:	Unstructured (UN)
	If the convergence cannot be attained with the unstructured correlation matrix, the following alternative structures will be attempted in the specified order: autoregressive(1) (AR(1)), and compound symmetry (CS). The first structure in this list with which the model converges will be used. If AR(1) structure is used, a random subject intercept will also be included in the model. This will need to be applied for each imputed dataset.
Equation	$Y_{ijkm} = \mu + \beta x_i + t_k + p_m + v_j + (tv)_{kj} + \alpha (xv)_{ij} + s_i + \varepsilon_{ijkm}$
•	where Y_{ijkm} is the change from baseline in frequency of HF to Week j for subject i (with treatment k and type of treatment m at baseline);
	μ is the intercept,
	β is the baseline covariate effect (baseline coefficient),
	x_i is the baseline frequency HF for subject i ,
	t_k is the fixed effect of treatment k (k = $Elinzanetant$, $placebo$),
	p_m is the fixed effect of type of treatment m at baseline $(m=Tamoxifen, Aromatase inhibitor)$
	v_j is the fixed effect of Week j ($j=1, 4, 8 & 12$),
	$(tv)_{jk}$ is the interaction effect of treatment k by Week j ,
	α is the covariate effect for the interaction (xv)
	$(xv)_{ij}$ is the interaction effect of baseline frequency HF of subject i by Week j ,

version 3.0 Page: 31 of 87

PROC MIXED data=DATA; CLASS subject treatment week pretreatment; MODEL change = baseline treatment week pretreatment treatment*week baseline*week /ddfm=KR outp=resid s; REPEATED week / subject=subject type=un; RANDOM subject; /* only if AR(1) covariance structure is used */ LSMEANS treatment*week /cl diff; ESTIMATE 'Elinzanetant - Placebo at Week 4' treatment 1 -1 treatment*week 0 1 0 0 0 -1 0 0 /cl; ESTIMATE 'Elinzanetant - Placebo at Week 12' treatment 1 -1 treatment*week 0 0 0 1 0 0 0 -1 /cl;		$s_i \sim \text{Normal } (0, \sigma_s^2) \text{ is the random effect of subject } i \text{ (only if } AR(1) \text{ covariance structure is used),}$ $\varepsilon_{ijklm} \sim \text{Normal } (0, \sigma^2) \text{ represents the residual variance component with corr } (\varepsilon_{ij}, \varepsilon_{ij}) = \rho_{jj}, j \neq j'.$
ODS OUTPUT TESTS3=TYPE3 LSMeans=LSMEAN ESTIMATES=ESTIM;	SAS code:	CLASS subject treatment week pretreatment; MODEL change = baseline treatment week pretreatment treatment*week baseline*week /ddfm=KR outp=resid s; REPEATED week / subject=subject type=un; RANDOM subject; /* only if AR(1) covariance structure is used */ LSMEANS treatment*week /cl diff; ESTIMATE 'Elinzanetant - Placebo at Week 4' treatment 1 -1 treatment*week 0 1 0 0 0 -1 0 0 /cl; ESTIMATE 'Elinzanetant - Placebo at Week 12' treatment 1 -1 treatment*week 0 0 0 1 0 0 0 -1 /cl;

A treatment policy strategy will be applied to handle all of the ICEs in this trial in the main estimand. According to this strategy, all collected data should be utilized in the analysis irrespective of occurrence of the ICEs.

Although all study participants are expected to be followed after ICEs, some missing data may occur. Missing values that occur while participants continue on their randomized treatment and simply represent missed assessments will be assumed missing at random (MAR). Such missing values could be intermittent or monotone and will be imputed using a Monte Carlo Markov Chain (MCMC) multiple imputation (MI) method. For the baseline value to be imputed, at least 2 post-baseline values out of the 4 post-baseline values (i.e., Week 1, 4, 8 & 12) need to be available. Possible missing baseline values will be imputed together with other intermittent missing values. Absolute values will be used for imputation steps.

Due to study design it will be difficult to implement a modelling approach aligned with the treatment policy strategy with the imputation model estimated from participants who discontinue the randomized treatment and provide data. The number of such participants is expected to be too small for estimating a robust imputation model. Therefore, the washout method will be used to impute missing data from participants who experience the ICEs (i.e. permanent treatment discontinuation) (Wang et al. 2023).

A placebo-effect is expected to be seen with the placebo group while the elinzanetant treatment effect will consist of both the placebo-effect and the effect of elinzanetant. The washout method effectively 'washes out' any pre-ICE treatment effect of elinzanetant in participants with an ICE randomized to elinzanetant, while modeling the mean placebo effect. Missing data in participants randomized to placebo will be assumed MAR.

version 3.0 Page: 32 of 87

For participants randomized to elinzanetant, the imputation model will have the dependent variable as the endpoint measurement at week 4 with the baseline measurement and the stratification factor, type of treatment of pre-existing condition, at baseline. The multiple imputation model will be estimated only based on placebo participants who remain in the study through week 4 and have available data at week 4. Similarly, week 1, 8 and 12 values missing after an ICE will be imputed using the same model specification but with endpoint measurement at week 1, 8 or 12, respectively, as the dependent variable.

The imputation will be done using a regression model (PROC MI with MONOTONE REG) including covariates described above for each time point and using the MNAR statement to estimate the model from placebo participants only.

To impute missing data for participants randomized to placebo, using MAR assumption, the imputation will be done using a regression model including measurements from all timepoints before the time-point being imputed in addition to baseline measurement and the stratification factor (PROC MI with MONOTONE REG).

PROC MI will be run with the random seed setting SEED=21656 to produce 500 imputed datasets.

After the completion of imputation step, change from baseline values will be calculated and each imputed dataset will be analyzed using the MMRM model specified in Table 4–3 to obtain an estimate of the mean change from baseline and of the treatment effect. The results will be combined using the Rubin's rule (Rubin, 1987) to obtain an overall estimated mean change from baseline and an overall estimated treatment effect. A total of 500 multiple imputation steps will be used.

Details regarding how the ICEs will be identified and specifics regarding the reasons for the occurrence of ICE are described in Section 6.4. All the ICEs will be reviewed prior to study unblinding.

The results from the main analysis will be presented as the number of participants, estimated mean change from baseline and standard error (SE) for each treatment group at Weeks 4 and 12 as well as the estimated treatment difference (elinzanetant - placebo), SE of the difference, associated 95% CI and P-value (one-sided). A plot of the model-based estimates with SE will be provided by the treatment for Weeks 4 & 12.

4.2.2. Sensitivity Analyses

4.2.2.1. Assessment of normality assumption

The assumption for normality in the main analysis (see Section 4.2.1) will be evaluated by graphical tools (i.e., qaplot and plot of residuals against predicted values). This will be assessed based on the observed data before multiple imputation is applied.

For the case of extreme violations of the normality assumption, a non-parametric rank ANCOVA will be carried out as sensitivity analysis and the Hodges-Lehmann estimate will be calculated as an estimate of the treatment effect (see Stokes et al. 2012). This will be carried out separately for the primary endpoints, change from baseline of HF frequency at Week 4 and at Week 12. Specifically, a Cochran-Mantel-Haenszel score test will be applied

version 3.0 Page: 33 of 87

to the residuals of a regression model on rank-transformed data while adjusting for baseline and the stratification factor.

The methodology described in Stokes et al. (2012) will be applied as follows using the SAS pseudo code given below. First, the values of the change from baseline variable as well as baseline covariate will be transformed to standardized ranks by stratification factor (pretreatment), using fractional ranks and mean method for ties:

Afterwards separate regression models will be fitted within each type of treatment of preexisting condition at baseline using the standardized rank values of the change from baseline and the baseline as dependent and independent variable, respectively. Residuals from these regression models will be captured for further testing of differences between treatment groups:

Finally, the stratified Cochran-Mantel-Haenszel (CMH) test using the values of the residuals as scores will be used to compare the two treatment groups:

The non-parametric rank ANCOVA described above will be applied to each imputation dataset within the multiple imputation procedure described earlier. Before combining the results of the CMH test using Rubin's rule, a normalizing transformation using the Wilson-Hilferty transformation as described in Ratitch, Lipkovich et al. (2013) will be applied. Let $cmh^{(m)}$ be the CMH statistic computed for the mth imputed dataset and df the corresponding degrees of freedom associated with the CMH statistic. The standardized test statistic for the mth imputation $st_cmh^{(m)}$ is then given by

$$st_cmh^{(m)} = \frac{\sqrt[3]{\frac{cmh^{(m)}}{df}} - \left(1 - \frac{2}{9 \times df}\right)}{\sqrt{\frac{2}{9 \times df}}}$$

The corresponding standard error is equal to 1. This standardized statistic together with its standard error will be passed on to PROC MIANALYZE to perform a combined CMH test using Rubin's rule.

version 3.0 Page: 34 of 87

In addition to the assessment of the treatment effect based on the CMH statistic as described above, the Hodges-Lehmann estimate of the median difference will be provided as estimate of the magnitude of the unadjusted treatment effect. The Hodges-Lehman estimate together with its asymptotic standard error will be computed for each imputation dataset and subsequently Rubin's rule will be used to combine the results. The Hodges-Lehmann estimate can be obtained using the following pseudo SAS code:

```
proc npar1way h1;
     class treatment;
     var change_from_baseline;
     output out=HL;
run;
```

The two-sided p-value based on the non-parametric rank ANCOVA, as well as the Hodges-Lehmann based estimate of the size of the treatment effect together with the corresponding standard error and 95 % confidence interval will be reported. To assess statistical significance the p-value from the non-parametric rank ANCOVA will be used.

4.2.2.2. Tipping point analysis

A tipping point analysis will be applied to assess the sensitivity of the main analysis results to modeling of the missing data that occur in presence of ICEs as described in Section 4.2.1. This will be done by applying an unfavorable additive shift (referred to as delta adjustment) to the values imputed by the MI model (with MONOREG) for the main analysis in the elinzanetant arm. For the endpoints related to the frequency of HF, the adjustments will be applied with delta values of 1, 2, 3, 4, etc. in each successive tipping point iteration until a tipping point is attained. Additional details on the tipping point sensitivity analysis are provided in Section 6.3.

4.2.3. Supplementary Analyses

Two supplementary estimands are defined for this trial.

The hypothetical strategy will be used for handling temporary treatment interruption and permanent treatment discontinuation due to COVID-19, administrative and any other treatment unrelated reasons in both supplementary estimands. Intake of prohibited medications, discontinuation in intake of adjuvant endocrine therapy and permanent treatment discontinuation with initiation of alternative VMS treatment will be handled by the hypothetical strategy in the first supplementary estimand and by the composite strategy in the second supplementary estimand.

4.2.3.1. First Supplementary Analysis

The information about ICEs and strategies to address them for the first supplementary estimands is provided in Table 4–4. The other estimand attributes are the same as for the main estimand (see section 1.1).

version 3.0 Page: 35 of 87

Table 4-4: First Supplementary Estimand: ICEs and Strategies to address them

ICEs ^a	Reason for ICE	Strategy	Data handling method
Temporary Treatment interruption ^b	AEs (treatment related/unrelated)	Treatment policy	Utilise the collected data after ICE.
	COVID-19 and administrative reasons	Hypothetical, If participant complied with treatment.	Model outcomes during the ICE under the hypothetical scenario.
Permanent discontinuation of randomized treatment	AEs (treatment related/unrelated) or Lack of efficacy		
	For participants who remained untreated/on background therapy.	Treatment policy	Utilise the collected data after ICE.
	For participants who initiate alternative VMS treatment	Hypothetical, If participant remained untreated.	Model outcomes after the ICE under the hypothetical scenario.
	Other treatment- unrelated reasons, including COVID-19	Hypothetical, If participant did not discontinue the randomized treatment.	Model outcomes after the ICE under the hypothetical scenario.
Intake of prohibited concomitant medication having impact on efficacy	All reasons	Hypothetical, If participant did not take prohibited concomitant medication/did not discontinued adjuvant endocrine therapy	Model outcomes under the hypothetical scenario during the period of confounding.
Interruption/Discontinu ation in intake of adjuvant endocrine therapy ^c	No reasons collected	Hypothetical, If a participant did not discontinue taking their adjuvant endocrine therapy	Model outcomes under the hypothetical scenario during the period of confounding.

ICE=Intercurrent event, AE=Adverse event, VMS = Vasomotor symptoms

Week 1 = Treatment taken on <5/7 days during week 1.

Week 4 = Treatment taken <80% during weeks 1-4 OR treatment taken on <5/7 days during either week 3 or 4. Week 8 = Treatment taken <80% during weeks 1-8 OR treatment taken on <5/7 days during either week 7 or 8.

Week 12= Treatment taken <80% during weeks 1-12 OR treatment taken on <5/7 days during either week 11 or 12.

For participants using tamoxifen: reduction of at least 50% of planned daily dosage taken during week 1, weeks 3 and 4, weeks 7 and 8 or weeks 11 and 12 compared to baseline

For participants using aromatase inhibitor: reduction of at least 30% of planned daily dosage taken during week 1, weeks 3 and 4, weeks 7 and 8 or weeks 11 and 12 compared to baseline

a) ICEs will be reviewed at the Blinded Review Meeting prior to the study unblinding

b) Definition of temporary treatment interruption:

c) Definition of interruption/discontinuation in intake of adjuvant endocrine therapy:

version 3.0 Page: 36 of 87

The details of data handling and missing data imputation for the first supplementary analysis of the primary endpoints are summarized in the Table 4–5. A pattern-mixture model using multiple imputation (MI) will be used to impute missing values that occur in presence of ICEs in a way that aligns with the ICE strategies.

The rows of Table 4–5 represent various patterns (subsets) of participants with a specific type of an ICE. For participants from each pattern who have missing data during the time frame of the ICE (Please see Sections 6.4.3 & 6.4.1 for the description of time frame for intake of prohibited medication and temporary treatment interruption ICEs. The time frame for the permanent treatment discontinuation is defined as the time after discontinuation.) or unobservable data under the assumed hypothetical scenario, a reference group is specified in the last column of the table.

Available data of participants from the corresponding reference group will be used to model the distribution of missing and unobservable data in each pattern. For the baseline value to be imputed, at least 2 post-baseline values out of the 4 post-baseline values (i.e. Week 1, 4, 8 & 12) need to be available. In case there are less than 10 participants with available post-ICE data in the defined reference group, at any intermediate time point, the missing data for that pattern will not be imputed at that time point. Additional details are provided in Section 6.2.

Table 4-5: First supplementary analysis data handling and missing data imputation strategy

Pattern ID	ICE and the associated reason	ICE strategy and data handling	Reference group for modeling the distribution of missing or unobservable data
1	Intake of prohibited medications Any reason	Hypothetical strategy If participant did not take prohibited concomitant medication. Discard the collected data after the intake of prohibited medication(s) for a certain time frame based on the medication class (See Section 6.4.2 for details).	Participants, from the same arm, who comply with treatment regimen ^b and have observed data at the time point that requires imputation.
	Temporary treatment interruption ^a	Hypothetical strategy If participant complied with treatment.	
	Due to COVID-19/ administrative or any other treatment unrelated reasons	Data collected for a specific assessment during/after a temporary treatment interruption will be discarded for that assessment Week only.	

version 3.0 Page: 37 of 87

2	Temporary treatment interruption ^a Due to AE	Treatment policy strategy Utilize all the collected data in the analysis.	Participants, from the same arm, who have available data before and during the treatment interruption. MI will be used to model change from a time point before treatment interruption to a time point with treatment interruption (Copy Increment from Reference imputation
3	Permanent treatment discontinuation	Treatment policy/Hypothetical strategy	Missing values that occur after the ICE will be imputed using a similar MI
	Due to AE/lack of efficacy	If participant remained untreated/on background therapy after permanent discontinuation of the randomized treatment, use the treatment policy strategy and utilize the collected data.	model as used in the main analysis of the primary endpoint, i.e., the wash-out method (Wang et al. 2023).
		Otherwise, if participant initiated an alternative treatment, use the hypothetical strategy under the hypothetical scenario "If participant did not initiate an alternative treatment after permanent discontinuation of randomized treatment". Discard data after the ICE.	
4	Permanent treatment discontinuation Due to COVID-19/ administrative or any other treatment unrelated reasons	Hypothetical strategy If participant did not discontinue the randomized treatment due to the specified reason. Any data collected after permanent treatment discontinuation will be discarded.	All other participants from the same arm (i.e., participants without a similar ICE at the time point that requires imputation).
	Interruption/Discontinuat ion in intake of adjuvant endocrine therapy	Hypothetical strategy If participant did not stop adjuvant endocrine therapy	
		Discard the collected data after the stop of adjuvant endocrine therapy.	

version 3.0 Page: 38 of 87

- a) If more than one interruption for different reasons is recorded during the specified weeks (please see the definition of ICE in Section 1.1), the data handling rule and missing data imputation will be performed based on the reason in the following pre-specified order: 1) AE, 2) Due to COVID-19/ administrative or any other treatment unrelated reasons.
- b) Complying with treatment regimen is defined as having no ICEs (i.e., no early discontinuation of randomized treatment, no treatment interruption in the respective week (definition in Table 1–2), no intake of prohibited concomitant medications and no reduction from baseline in adjuvant endocrine therapy).

Missing values that occur in the time frame outside of any identified ICE and simply represent missed assessments will be assumed missing at random (MAR). Such missing values are likely to be intermittent and will be imputed using a Monte Carlo Markov Chain (MCMC) MI method for imputation of non-monotone missing data. Additional details are provided in Section 6.2.

A pattern-mixture model using multiple imputation will be applied to impute missing and unobservable data to mimic the distribution of observed data in the appropriate reference group as described in Table 4–5, conditional on covariates and partially observed data. The imputations will be done sequentially in patterns 1 through 4. The reference group for imputation in patterns 3 and 4 may contain participants who have some values imputed during the imputation of preceding patterns. Consequently, the MI model for pattern 4 will reflect a mixture of participants, some of which fully comply with the randomized treatment and some with other types of ICEs. Additional details of the pattern-mixture modeling with multiple imputation are provided in Section 6.2.

Each imputed dataset will be analyzed using the MMRM model specified in Table 4–3 to obtain an estimate of the treatment effect. The results will be combined using Rubin's rule (Rubin, 1987) to obtain an overall estimated treatment effect.

The same baseline covariates will be included in the imputation and the analysis step as specified in Section 4.2.1.

The results from the supplementary analysis will be presented in a similar way as to the main analysis (see Section 4.2.1).

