4.1.2. Data Rules

Definition of baseline: The latest available valid measurement excluding unscheduled measurements at or before the start of treatment (for treated subjects) / randomization date (for randomized but not treated subjects). If the last observation available prior to randomization is the measurement from the Screening Visit, this would be used as the baseline value. In case a wash-out period was necessary, measurements taken during the prescreening visit will not be used as a baseline value unless specified otherwise.

Change from baseline: To calculate the absolute change from baseline the baseline value will be subtracted from the value under treatment/follow-up, i.e.,

Absolute change = post baseline value – baseline value.

Some parameters will be additionally analyzed as relative change defined as

Relative change = 100 * [(post baseline value – baseline value) / baseline value].

Derivation of intercurrent event (ICE): Intercurrent events that occurred from randomization date (for randomized but not treated subjects) / start of treatment (for treated subjects) to day 84 inclusive will be flagged.

version 3.0 Page: 24 of 87

For the "permanent discontinuation of randomized drug", "intake of prohibited medication having impact on efficacy" and "interruption/ discontinuation in intake of adjuvant endocrine therapy", if the ICE occurs on or before the 5th day of the week, it will be flagged for the respective week. If the ICE occurs on the 6th or 7th day of the week, it will be flagged from the following week. For example, if the participant permanently discontinues from the randomized drug on the 2nd day of week 4, the ICE will be flagged from week 4 onwards. If the discontinuation from the randomized drug occurs on the 6th day of week 4, then the ICE will be flagged from week 5 onwards. For the ICEs "intake of prohibited medication having impact on efficacy" and "interruption/ discontinuation in intake of adjuvant endocrine therapy", if the end date for the impact on efficacy occurs on the 1st or 2nd day of the week, the respective week should not be flagged. If the end date of impact on efficacy occurs on or after the 3rd day of the week, the week should be flagged.

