Intake of prohibited concomitant medication having impact on efficacy	All reasons	Composite Treatment failure (i.e. no change from baseline)	Model outcomes under the treatment failure during the period of confounding.
Interruption/Disc ontinuation in intake of adjuvant endocrine therapy ^c	No reasons collected	Composite Treatment failure (i.e. no change from baseline)	Model outcomes under the treatment failure during the period of confounding.

ICE=Intercurrent event, AE=Adverse event, VMS = Vasomotor symptoms

- a) ICEs will be reviewed at the Blinded Review Meeting prior to the study unblinding
- b) Definition of temporary treatment interruption:
 - Week 1 = Treatment taken on <5/7 days during week 1.
 - Week 4 = Treatment taken <80% during weeks 1-4 OR treatment taken on <5/7 days during either week 3 or 4.
 - Week 8 = Treatment taken <80% during weeks 1-8 OR treatment taken on <5/7 days during either week 7 or 8.
 - Week 12= Treatment taken <80% during weeks 1-12 OR treatment taken on <5/7 days during either week 11 or 12.
- c) Definition of interruption/discontinuation in intake of adjuvant endocrine therapy:
 For participants using tamoxifen: reduction of at least 50% of planned daily dosage taken during week 1, weeks 3 and 4, weeks 7 and 8 or weeks 11 and 12 compared to baseline

version 3.0 Page: 41 of 87

For participants using aromatase inhibitor: reduction of at least 30% of planned daily dosage taken during week 1, weeks 3 and 4, weeks 7 and 8 or weeks 11 and 12 compared to baseline

Table 4–7: Second supplementary estimand data handling and missing data imputation strategy.

Pattern ID	ICE and the associated reason	ICE strategy and data handling	Reference group for modeling the distribution of missing or unobservable data
N/A	Intake of prohibited medications and Interruption/Discontinuation in intake of adjuvant endocrine therapy ° Any reason	Composite strategy Treatment failure (i.e. no change from baseline.) Discard the collected data after the intake of prohibited medication(s) for a certain time frame based in the medication class (See Section 6.4.3 for details) and assign the value of zero change from baseline. Discard the collected data after interruption/discontinuation of adjuvant endocrine therapy and assign the value of zero change from baseline.	N/A

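### For endocrine-therapy interruption, the supplementary estimand tables limit the event to a period of confounding, but the data-handling tables discard later data with no end, and that period is never defined.

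*SAP*

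**What the plan says.** The SAP describes this event in two ways.

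*With an end:*
- Table 4-4 (first supplementary estimand, hypothetical strategy): "Model outcomes under the hypothetical scenario during the period of confounding".
- Table 4-6 (second supplementary estimand, composite strategy): "Model outcomes under the treatment failure during the period of confounding".
- Section 4.1.2 names this event in its week-flagging rule. Its condition and result read: "end date for the impact on efficacy occurs on the 1st or 2nd day of the week, the respective week should not be flagged". From the third day on, the week is flagged.
- Section 6.4.4 compares intake with baseline in separate windows: Week 1, Weeks 3-4, Weeks 7-8 and Weeks 11-12.

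*Without an end:*
- Table 4-5, pattern 4: "Discard the collected data after the stop of adjuvant endocrine therapy".
- Table 4-7: "Discard the collected data after interruption/discontinuation of adjuvant endocrine therapy and assign the value of zero change from baseline".

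Other rules in the same tables do state limits. Table 4-7 discards data after prohibited medication "for a certain time frame based in the medication class". In Table 4-5, data affected by a temporary interruption of study drug for treatment-unrelated reasons "will be discarded for that assessment Week only".

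**The concern.** An estimand table says which outcomes an event affects, and a data-handling table says which records are removed. For this event the two differ on duration. A programmer working literally from Tables 4-5 and 4-7 would treat a brief lapse in tamoxifen or aromatase inhibitor intake like a permanent stop. Later diary data would be imputed in the first supplementary analysis and set to zero change in the second. A programmer working from Section 4.1.2 would use observed data again once the impact had ended. Two pre-specified analyses of the primary endpoints therefore lack a unique result. Section 4.3.1.4 carries both estimands over to PROMIS SD SF 8b and MENQOL, so the ambiguity applies there too.

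**Working it through.** **1. Is an end of the event defined?** Section 4.2.3.1 gives or points to time frames for prohibited medication, temporary study-drug interruption and permanent discontinuation. It gives none for endocrine therapy. Section 6.4.4 gives the thresholds and windows but no duration of impact, and it does not tie each window to an analysis week as Section 6.4.1 does for study drug. So Section 4.1.2 relies on an end date that the SAP never derives for this event.

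**2. Worked case.** A tamoxifen user takes less than half her planned dosage in Weeks 3-4 (to Day 28) and resumes fully on Day 29. Week 8 is Days 50-56 and Week 12 is Days 78-84. Under Section 4.1.2 a week is unflagged if the impact ends by its second day, which is Day 51 for Week 8 and Day 79 for Week 12.

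| Impact ends | Tables 4-4 and 4-6 with Section 4.1.2 | Table 4-5, read literally | Table 4-7, read literally |
|---|---|---|---|
| By Day 51 | Weeks 8 and 12 observed | both imputed | both zero change |
| Days 52-79 | Week 8 flagged, Week 12 observed | both imputed | both zero change |
| Day 80 or later | both flagged | both imputed | both zero change |

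The rules disagree in the first two rows and agree in the third. The SAP does not say which row applies.

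**3. Scale for comparison.** Inputs from SAP Section 5: Week 12 SD 4.29, N = 243 and 122, one-sided alpha 0.025.
- SE = 4.29 × √(1/243 + 1/122) = 4.29 × 0.1110 = 0.476.
- Check: at a difference of -1.50 the noncentrality is 1.50 / 0.476 = 3.15. With 363 degrees of freedom the power is 88.16%, as Table 5-1 states.

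**4. Second supplementary estimand, Week 12.** Let a share f of each arm have an interruption that resolves early enough for Week 12 to be kept under the time-limited rule. Setting these women to zero multiplies each arm mean by (1 - f). The rates and mean changes below are assumptions, since the documents give neither.
- Changes -6 and -4, f = 1%: means -5.94 and -3.96. The difference goes from -2.00 to -1.98, a shrinkage of 0.02.
- Same changes, f = 5%: means -5.70 and -3.80. The difference is -1.90, a shrinkage of 0.10, or 0.10 / 0.476 = 0.21 SE.
- True difference -1.50, f = 5% in the elinzanetant arm only: with placebo -3, 0.95 × (-4.5) + 3 = -1.275; with placebo -7, 0.95 × (-8.5) + 7 = -1.075. The shift is 0.225 to 0.425.
- Same, f = 5% in the placebo arm only, placebo -3: -4.5 - 0.95 × (-3) = -1.65, so the difference widens.

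**5. First supplementary estimand.** Discarded values are imputed from other women in the same arm, so the shift depends on how far the resumers differ from them. The documents give no basis for a figure.

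**The case against.** The best defence is that Section 4.1.2 is the general flagging rule and already covers this event (the version history records its addition in version 2.0). On that view the cells in Tables 4-5 and 4-7 are shorthand for the flagged weeks. Section 6.2 also starts pattern 4 with an MCMC step for intermittent gaps, so retained later values are not impossible to handle. This does not remove the conflict. Neither table refers to Section 4.1.2 for this event, other rows spell out their limits, and Section 6.2 goes on to treat the remaining pattern 4 data as monotone, which suits discarding to the end. Reading *stop* as a permanent stop does not help either, because the Table 4-5 row covers interruption too and Table 4-7 names it.

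A second defence is that the Variable attribute in Section 4.2.3.2 gives zero change whenever such an event is not absent, with no time limit, which agrees with Table 4-7. But that attribute treats prohibited medication identically, and Table 4-7 still limits prohibited medication in time. The attribute does not settle duration.

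What does stand is a limit on the claim. A reader might infer that the estimand tables definitely keep the Week 8 and Week 12 values of a woman who resumes. They do not establish that, because the period of confounding is undefined and could extend past either week.

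**Conclusion.** The inconsistency is real and should be corrected. Literal use of Tables 4-5 and 4-7 need not reproduce what Tables 4-4 and 4-6 describe, and the missing definition means the SAP cannot settle the matter.

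The reach is limited to the two supplementary estimands. A reader might infer that the Week 12 primary result is compromised. It is not: the main estimand applies treatment policy to every event and uses all collected data, and the fixed-sequence tests do not involve the supplementary analyses.

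The size is unknown. With equal assumed rates of 1-5% and assumed changes of -6 and -4, the second supplementary difference moves towards zero by 0.02-0.10 hot flashes per day, small beside an SE of about 0.48. Unequal rates could move it further, in either direction. These figures assume that every such woman's Week 12 value would otherwise be kept. If the period of confounding reaches Week 12, the discrepancy at that week disappears.

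**What to change.** Before unblinding:

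1. In Section 6.4.4, define the period of confounding for this event, including how its end date is derived, and tie each intake window to its analysis week (1, 4, 8 or 12), as Section 6.4.1 does.
2. In Tables 4-5 and 4-7, replace the open-ended wording with: *for the analysis weeks flagged for this ICE under Sections 4.1.2 and 6.4.4*. State that observed data are used in unflagged weeks.
3. In Section 6.2, let the pattern 4 step handle non-monotone gaps, so that values observed after a resolved interruption are kept.

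If the intention is to discard everything after the event, say so in Tables 4-4 and 4-6 and in Section 4.1.2 instead, and remove the end-date rule for this event.

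Either route costs a few lines of SAP text and matching program specifications. No new data are needed, because daily background-medication intake is already recorded in the eDiary.
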